The secondary aims of this study are to 1) assess provider confidence with delivery of the impacted fetal head before and after participating in simulation education and 2) assess change in maternal and perinatal morbidity of additional secondary outcomes, 3) assess the association of duration of second stage and maternal and perinatal outcomes.

- Research question 2.1: Does Regions hospital provider and team confidence regarding delivery of impacted fetal head increase after participating in simulation education?
- Research question 2.2: Does implementation of a simulation protocol that addresses delivery of the impacted fetal head decrease morbidity of other individual secondary outcomes (see variables table) of cesarean delivery during the second stage of labor at Regions Hospital compared to morbidity over the same time period at Methodist Hospital?
- Research question 2.3: Is duration of second stage related to maternal and perinatal complications?

3. Background, Rationale, Significance

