Members of the study team have verified the accuracy of this method of identifying cesarean section during the second stage of labor by cross-checking a Clarity pull of EMR data with chart audit for a random sample of 10 patients.

Medical staff inclusion criteria: all 120 staff members (staff physicians, residents, nurses, surgical technicians) at Regions hospital who practice in the Birth center who underwent required simulation education regarding delivery of deeply impacted fetal heads during second stage cesarean section (50 physicians and 65 nurses and 5 techs) and completed the surveys as part of the QI simulation project.

ii. Sample size

Patients: A data pull conducted by an HP Institute RIIS programmer in September 2017 indicated that there are 80 patients per year at Regions hospital having second stage cesarean sections and 80 patients per year at Methodist hospital having second stage cesarean sections. This study will gather data via programming and chart audit on the following counts of patients in these time period:

- A. July 1, 2014 – June 30, 2015 (80 Regions patients)
- B. July 1, 2015 – June 30, 2016 (80 Regions patients)
- C. July 1, 2016 – December 31, 2017 (120 Regions, 120 Methodist) - 18 mo PRE period
- D. January 1, 2018 – June 30, 2019 (120 Regions, 120 Methodist) - 18 mo POST period

Different subsets of patients will be used for different research questions. For research questions 1.1, 1.2, 2.2 Group C above will serve as the pre-period patients and Group D for post-period patients. Thus, the total patient sample size for these research question is expected to be n=480. For research question 2.3, in addition to Groups C and D, we will also include utilize the 160 patients from Regions in Groups A and B for a sample size of 400 at Regions and 240 at Methodist (n=640 total).

Medical staff sample size: The simulation center staff will survey 120 staff (50 physicians, 65 nurses, and 5 techs) immediately before and after the required simulation education as part of an existing QI project. This QI project data will be used to address

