Research question 1.2: Does the simulation protocol decrease a composite variable of infant morbidity defined as a) 5 minute APGARs <7, b) NICU admission, c) umbilical cord arterial pH <7.1, and d) fetal injury, at Regions Hospital compared to morbidity over the same time period at Methodist Hospital?

Analytic sample: 480 infant patients (120 Regions before/120 after simulation; 120 Methodist before/120 after simulation). Each sample of 120 is viewed as an independent sample.

Analytic approach: Same as 1.1, but uses the endpoint of composite infant morbidity

Research question 2.1: Does Regions hospital provider and team confidence regarding delivery of impacted fetal head increase after participating in simulation education?

Analytic sample: The 120 staff completing the pre and post simulation surveys, and sample of 80 completing the pre and 6 month surveys. This data is obtained from surveys from the QI project utilizing the required simulation training events.

Analytic approach: Descriptive statistics (mean, proportion) and 95% CIs will be used to summarize staff survey items at each time point, and change from pre-simulation to immediately post-simulation, and pre-simulation to 6 month post-simulation. Plots over time of key survey items will illustrate staff reactions and perceptions over time. Simple paired-data analyses (e.g., paired t-tests, McNemar's test) may be used to test change over time in key items or composites specified a-priori. Where possible, composites of multiple items will be summarized rather than individual items to reduce the number of comparisons and tests made.

Research question 2.2: Does implementation of the simulation protocol decrease morbidity of other individual secondary outcomes (see variables table) during the second stage of labor at Regions Hospital compared to morbidity over the same time period at Methodist Hospital?

Analytic sample: 480 infant/maternal patients (120 Regions before/120 after simulation; 120 Methodist before/120 after simulation). Each sample of 120 is viewed as an independent sample.

Analytic approach: Same as 1.1, but dependent variables for these analyses will include the individual component items of the primary endpoints, and variables listed as “secondary endpoints” in the variable table. Due to the large number of tests conducted, these analyses will be viewed as more exploratory.

Research question 2.4: Is duration of second stage related to maternal and perinatal complications?

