Analytic sample: 640 infant/maternal patients at Regions and Methodist seen June 2015-June 2019.

Analytic approach: Within each hospital (Regions, Methodist), duration of second stage will be stratified (<1 hour, 1-2 hrs, 2-3 hrs, 3-4 hrs, >4 hours). Individual maternal and infant endpoints in the variable table above will be summarized in terms of mean and proportion and 95% CIs within the strata. This analysis is considered descriptive and exploratory.

g) Power analysis: Based on recent literature (Laughton, 2014; Vousden 2014, Kawakita 2017), the estimate of the composite maternal endpoint for research question 1.1 ranges from 20% (if all elements of the composite are completely overlapping) to 40% (if all elements of the composite are independent and additive). Making the simplifying assumptions that Regions and Methodist have the same morbidity in the pre-period, and that Methodist morbidity will not change from the pre to post-period, this study is powered at 80% (alphas=.05, 2-sided) to detect a difference in the Methodist and Regions maternal morbidity composite of 20% (Methodist) vs. 8% (Regions); 30% vs. 15%, or 40% vs. 23%, using a logistic regression model. Similar assumptions could be applied to the infant composite endpoints. For the staff survey, the study is powered to detect a change in a continuous survey item (e.g., staff confidence in handling the procedure) from one time point to a later time point of 0.26 standard deviation units for the sample of n=120 (pre to post simulation) and 0.32 standard deviation units for the sample of n=96 (pre to 6 months, or post to 6 months).

h) Strengths and limitations

Strengths: Large N, broad availability of data elements, comparison group (Methodist Hospital) for more carefully assessing the effect of the QI project simulation training, enthusiastic buy-in by OB/GYN area in Regions, required QI project simulation training so all staff are exposed to simulation.

Limitations: Lack of randomization, elements in chart might not be complete, two hospital systems might not be completely comparable, unknown baseline level of primary endpoints.

5. *Setting/Environment/Organizational feasibility*

The Regions Hospital birth center team delivers about 2400 babies a year. The staff and providers involved in cesarean sections are a relatively stable population. We do not have

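### The plan asks whether second-stage duration is associated with complications, but reports only ten separate stratum summaries and no measure of association

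*Combined protocol and SAP*

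**What the plan says.** Section 2 (Study Aims) sets out, as the third secondary aim, to "assess the association of duration of second stage and maternal and perinatal outcomes". The matching question reads "Is duration of second stage related to maternal and perinatal complications"; it is numbered 2.3 in the aims and 2.4 in section 4 f.

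The sample-size text in section 4 b gives this question the largest sample in the study, a "sample size of 400 at Regions and 240 at Methodist (n=640 total". It gets there by adding the "160 patients from Regions in Groups A and B" to the 480 used for the other patient-level questions.

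The analysis in section 4 f is done separately at each hospital: "duration of second stage will be stratified (<1 hour, 1-2 hrs, 2-3 hrs, 3-4 hrs, >4 hours". Individual endpoints from the variables table are then "summarized in terms of mean and proportion and 95% CIs within the strata". The plan adds: "This analysis is considered descriptive and exploratory". It specifies no model, trend, between-stratum contrast, combination over hospitals or adjustment for period. The variables table in section 4 d lists length of second stage as continuous, taken from the EMR.

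**The concern.** An association question needs a quantity that expresses the association: an odds ratio or mean difference per hour, a trend, or at least a stated contrast with an interval. Ten separate estimates per endpoint leave the reader to judge a gradient by eye.

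Three features make that hard. Each stratum holds a fraction of the cohort, so its interval is wide. Information on the same gradient from the two hospitals is never combined. Pre- and post-training patients are pooled within strata, although the study's own hypothesis is that training lowers morbidity at Regions; if the mix of durations also differed between periods, the crude Regions strata would blend a period effect with a duration effect.

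The 160 patients in Groups A and B, a quarter of the 640, are included for this question alone. Their information would not be gathered into any single estimate.

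**Working it through.** **1. Sample size.** Groups A to D in section 4 b: 80 + 80 + (120 + 120) + (120 + 120) = 640, with 80 + 80 + 120 + 120 = 400 at Regions and 120 + 120 = 240 at Methodist. The plan's figure reproduces. Counting A and B as pre-training, Regions has 280 pre and 120 post; Methodist has 120 and 120. No power or precision is stated for this question.

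**2. Stratum size.** The documents give no duration distribution. If the five bands were equal, strata would hold 400/5 = 80 at Regions and 240/5 = 48 at Methodist.

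**3. Precision.** Half-width = 1.96 × √(p(1−p)/n). The 20–40% range is the one that section 4 g gives for the maternal composite, used here as an illustration.

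| n | p = 20% | p = 30% | p = 40% |
|---|---|---|---|
| 80 (Regions stratum) | 8.8 points | 10.0 | 10.7 |
| 48 (Methodist stratum) | 11.3 | 13.0 | 13.9 |
| 640 (all patients) | 3.1 | 3.6 | 3.8 |

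Example: 1.96 × √(0.2 × 0.8/80) = 0.088. Unequal bands make the small strata worse: 16.0 to 19.6 points with 24 patients. For a rarer individual endpoint at 5%, the half-width is 4.8 points (n = 80) or 6.2 points (n = 48), about as large as the rate itself.

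**4. What two strata could separate.** With a two-sided 5% test and 80% power, two strata of 80 distinguish 20% from 40%, 30% from 52%, or 40% from 62%. Two strata of 48 distinguish 20% from 47%, 30% from 58%, or 40% from 68%.

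**5. What one combined estimate could do.** This is a simulation under assumptions that are not in the documents: 400 + 240 patients, gamma-distributed duration (mean 2.5 h, SD 1.4 h), odds ratio 1.2 per hour, two-sided 5% level, event rates 20–40%.

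- Linear duration term, all 640 patients: about 73–93% power.
- Within-hospital test of <1 h against >4 h: about 32–48% at Regions and 22–35% at Methodist.

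At a 30% event rate the linear term has about 84% power, a trend over the same five bands combined across hospitals about 80%, and a two-degree-of-freedom spline test about 77%.

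**6. Where the loss arises.** A linear trend score over the five bands keeps about 96% of the information in continuous duration if durations are uniform over 0–5 h, and about 83% under a gamma distribution with mean 3 h. Banding therefore costs little. The loss comes from never combining the strata.

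**The case against.** The strongest defence is that the plan calls this analysis descriptive and exploratory, plans no test and claims no power. Ordered bands by hospital show the shape of the relationship without a model, and they respect the limitation stated in section 4 h that the hospitals may not be fully comparable. This stands as a reason to keep the table. It does not supply a measure of association, and an exploratory label does not rule one out: Research question 2.2 is also exploratory, yet uses the regression of Research question 1.1.

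A second defence is that duration is listed as a covariate, so a duration coefficient could appear in the models for 1.1, 1.2 and 2.2. That is possible, but only if the covariate is judged necessary, and only in 480 patients without Groups A and B. It is not the analysis named for this question.

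A reader might infer that the plan discards most of the power of 640 patients. The documents do not support that. There is no planned test whose power could be lost, and any comparison depends on an assumed duration distribution, effect and contrast. With durations uniform over 0–5 h and odds ratios of 1.20–1.25 per hour, the extreme-band test at Regions alone has 43–79% power against 74–98% for the combined slope, so it keeps more than half. Requiring two 95% CIs not to overlap would exaggerate the gap: with equal standard errors that corresponds to a level of about 0.006.

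A reader might also object that a value of exactly 2 hours fits two bands. This is ordinary shorthand, and section 4 c leaves operational definitions to the programmer and clinical staff.

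**Conclusion.** The concern holds in a limited form. The stated aim and question ask for an association; the planned analysis gives ten imprecise stratum estimates per endpoint, pooled over periods, and no measure of association. The imprecision is about ±9 to 11 points at Regions and ±11 to 14 at Methodist, given equal strata and event rates of 20–40%.

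The power figures only illustrate what combining the strata could gain, since the documents give neither a duration distribution nor an effect size. They also take the 640 as stated. Section 4 f dates this sample from June 2015, whereas 640 requires Group A from July 2014; without Group A the total is 640 − 80 = 560, and linear-term power at a 30% event rate falls to about 79%.

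This is a worthwhile, low-cost improvement to an exploratory secondary analysis. It does not affect the primary questions.

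**What to change.** - Keep the hospital-by-duration table as description.
- Add one exploratory regression per endpoint: logistic for the two composites and for binary endpoints with enough events, linear for continuous endpoints. Enter duration as a continuous linear term, adjusted for hospital, period and hospital × period, with Groups A and B coded as pre-training.
- Report the odds ratio, or mean difference, per hour of second stage with its 95% CI.
- Use a restricted cubic spline with three knots only as a check for non-linearity. A spline has no single odds ratio per hour, so it should not replace the linear term as the reported summary.
- State that these models are exploratory and carry no multiplicity control.
- Reconcile the question number (2.3 or 2.4) and the sample dates in the same edit.

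The cost is a few lines of SAP text and code on data already being collected. The downside is a further set of exploratory models resting on a linearity assumption, which the spline checks.

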The timeline of the simulation will be as follows: Pre simulation survey- 10 min, ACOG second stage cesarean section slide presentation- 20 min, practice with mannequins (separate for nursing and physician providers based on skill sets required)- 40 mins, combined second stage cesarean section scenario with whole team with debrief- 40 min, Post simulation survey- 10 min. This simulation will be based on a presentation given at the ACOG meeting in 2016. Simulations will be led by [name], [name], [name], and [name] from mid October 2017 through mid-December 2017 in the simulation center at Regions hospital.

All birth center team members will be notified regarding the simulation events by email and at staff meetings and will be required to attend 1 simulation event from mid-October-December 2017. Three additional simulation events will be offered during the project period for new Birth Center staff.

4. Approach

a. Study design: This study is an observational, time (pre vs. post simulation) by group (Regions vs. Methodist) design using a retrospective programmatic and manual chart review to evaluate the morbidity of second stage cesarean deliveries before and after implementation of

simulation education at Regions Hospital from July 2014 to June 2019. The same morbidity metrics will be gathered from patients at Methodist Hospital during the same pre and post-time periods to serve as a comparison group. Differential pre-post change in morbidity across patients at the two sites will serve as the key comparison. We will also assess staff confidence and change in self-confidence in the management of impacted fetal head using data from pre and post simulation Quality Improvement project surveys.

b. Population

i. Inclusion/Exclusion criteria:

Patient inclusion: The patient study population includes all patients age 18-45 who underwent cesarean section during the second stage of labor (during the time period July 2014-June 2019 at Regions hospital and Methodist hospital). Second stage is defined as the time between complete cervical dilation and delivery of the infant. Exclusion criteria include patients who underwent cesarean section in second stage for malpresentations (i.e., breech and noncephalic presentations), patients who underwent cesarean section prior to 37 weeks gestation, and patients on the exclusion list for research.

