Staff survey: The pre and post staff surveys are used for the QI project to assess staff perceptions of the required simulation training, and are included as the end of the narrative as appendices. These surveys use items developed for this project rather than existing tools. Surveys include a label to identify whether they are gathered before or after the simulation, and contain items such as confidence in handling second stage cesarean sections.

f) Statistical analysis plan

Descriptives (mean, standard deviation, proportion) and frequency distributions of all variables will be computed and examined for distribution shape, outliers, missing data, and implausible data. Tables of descriptive statistics summarizing patients in both care systems (Regions, Methodist)

will be created. Because there are only 2 primary outcomes (both of which are composite variables), there will be no control for multiple testing. Inferential analysis of secondary endpoints will be considered exploratory with the known limitation that multiple testing could yield type 1 errors. Covariates in regression analysis will be specified a-priori on the basis of theory and when such covariates are unbalanced in comparison groups.

Research question 1.1: Does the simulation protocol decrease a composite variable of maternal morbidity defined as a) extension of uterine incision, b) operative blood loss > 1000 mL, c) requirement of transfusion, d) wound infection within 6 weeks, and d) endometritis within 6 weeks, at Regions Hospital compared to morbidity over the same time period at Methodist Hospital?

Analytic sample: 480 maternal patients (120 Regions before/120 after simulation; 120 Methodist before/120 after simulation). Each sample of 120 is viewed as an independent sample.

Analytic approach: Logistic regression will be used to predict the composite maternal morbidity endpoint (0/1) from hospital (Regions, Methodist), time (pre or post simulation), and their interaction. Covariates will be included if needed as described earlier. Model-based proportions, standard errors, and 95% CIs for each hospital for each time point, change over time, and differential change over time by hospital will be computed. A significant hospital * time interaction and pattern of effects showing more improvement over time in Regions than Methodist will support the underlying hypothesis of differential improvement over time favoring Regions and potentially due to the effects of the simulation.

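### The stated 80% power fits a comparison of two groups of 120; the hospital-by-time interaction that the plan tests has about 53–55% power for the same three effects

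*Combined protocol and SAP*

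**What the plan says.** Section 4.g (Power analysis) states that "this study is powered at 80% (alphas=.05, 2-sided) to detect a difference in the Methodist and Regions maternal morbidity composite". Three scenarios follow, each setting a Methodist rate against a lower Regions rate: "20% (Methodist) vs. 8% (Regions); 30% vs. 15%, or 40% vs. 23%, using a logistic regression model". Two conditions, which the plan itself describes as simplifying, underlie the figure: "Regions and Methodist have the same morbidity in the pre-period, and that Methodist morbidity will not change from the pre to post-period". The section names no formula, does not say which groups are compared, and gives no number per group for this figure.

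The analysis to which the figure should apply is set out elsewhere. Section 4.a (Study design) says: "Differential pre-post change in morbidity across patients at the two sites will serve as the key comparison". For research question 1.1, section 4.f gives the sample as "480 maternal patients (120 Regions before/120 after simulation; 120 Methodist before/120 after simulation", treated as independent samples. It then fits a logistic regression on hospital, time and their interaction, and gives the criterion: "A significant hospital * time interaction and pattern of effects showing more improvement over time in Regions than Methodist will support the underlying hypothesis". The same section plans "Model-based proportions, standard errors, and 95% CIs for each hospital for each time point, change over time, and differential change over time by hospital".

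For the infant composite, section 4.g says only: "Similar assumptions could be applied to the infant composite endpoints".

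**The concern.** The power statement describes a difference between two rates, one per hospital. The planned test compares two changes, each of which is itself a difference between two estimated rates. A difference of differences has a larger variance than a single difference at the same number per group. A power figure for the single comparison therefore overstates the power of the interaction.

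The assumptions of equal pre-period rates and no change at Methodist do not close the gap. They fix the true size of the effect. The model still estimates both pre-period rates from 120 patients each, and that sampling error enters the interaction.

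What is at stake is how the primary result is read. With a stated power of 80%, a reader is likely to take a non-significant interaction as fair evidence against effects of the sizes named. If the true power is near 54%, such a result is almost as likely as a significant one when the effect is real. The limitations in section 4.h do not mention power, and its list of strengths counts the sample size as large.

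**Working it through.** **Inputs.** Two-sided alpha 0.05 and the three pairs of rates (section 4.g); 120 patients in each of four independent groups (section 4.f). The assumptions in section 4.g fix all four true rates: Regions pre, Methodist pre and Methodist post all equal p0 (20%, 30% or 40%), and Regions post equals p1 (8%, 15% or 23%). No outside figure is needed.

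**Step 1: reproduce the stated 80%.** Take two groups of 120 and a pooled z test: power = Φ{[(p0 − p1) − 1.96·√(2·p̄(1 − p̄)/120)] / √([p0(1 − p0) + p1(1 − p1)]/120)}, where p̄ is the mean of p0 and p1.

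- 20% vs 8%: (0.12 − 1.96 × 0.0448)/0.0441 = 0.73, power 76.7%.
- 30% vs 15%: power 79.8%.
- 40% vs 23%: power 81.3%.

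The Regions rates that give exactly 80% by this formula are 7.6%, 15.0% and 23.3%, which round to the three rates in the plan. Other readings do not give 80%: 240 vs 240 gives 97–98%, Regions post against the other three groups pooled gives 90–94%, and the hospital main effect gives 42–49%.

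**Step 2: power of the planned interaction.** The effect is logit(p0) − logit(p1). Its variance is 3/[120·p0(1 − p0)] + 1/[120·p1(1 − p1)]; the two-group variance has 1 in place of 3. Power = Φ(effect/SE − 1.96).

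| | 20% vs 8% | 30% vs 15% | 40% vs 23% |
|---|---|---|---|
| Effect (log odds ratio) | 1.056 | 0.887 | 0.803 |
| Interaction variance | 0.15625 + 0.11322 = 0.2695 | 0.11905 + 0.06536 = 0.1844 | 0.10417 + 0.04705 = 0.1512 |
| Two-group variance | 0.1653 | 0.1050 | 0.0818 |
| Ratio of variances | 1.63 | 1.76 | 1.85 |
| Interaction z | 2.03 | 2.07 | 2.06 |
| **Power, Wald formula** | **53.0%** | **54.2%** | **54.2%** |
| Power, simulated Wald (400,000 data sets) | 53.6% | 54.7% | 54.5% |
| Power, simulated likelihood ratio (100,000 data sets) | 55.1% | 55.4% | 55.2% |

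A one-sided test would reach only 65–66%, and the plan specifies two-sided.

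**Step 3: what 120 per group can detect.** By the Wald formula, 80% interaction power needs Regions post-period rates of 4.6%, 10.7% and 17.8% (interaction odds ratios of about 0.19, 0.28 and 0.32). At the rounded rates of 5%, 11% and 18%, the simulated Wald test gives 80.7%, 80.1% and 80.2% (odds ratios of about 0.21, 0.29 and 0.33); the formula gives 77.2%, 78.6% and 79.2%. To have 80% power for the plan's own pairs would take about 228, 221 and 221 patients per group, instead of 120.

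**Step 4: expected precision.** The 95% CI half-width for the differential change in proportions is 1.96·√{[3·p0(1 − p0) + p1(1 − p1)]/120}.

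- 20% vs 8%: 1.96·√(0.5536/120) = 13.3 points, against a true difference of 12.
- 30% vs 15%: 1.96·√(0.7575/120) = 15.6 points, against 15.
- 40% vs 23%: 1.96·√(0.8971/120) = 16.9 points, against 17.

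**The case against.** Several points can fairly be made for the plan.

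- **The origin of the 80% is an inference.** The section says a logistic model was used. The nearest two-group equivalent, a Wald test of the log odds ratio, gives 73.8%, 78.2% and 80.2%. The pooled z test fits better, but the first pair fits only after rounding. This stands, so the two-group origin is the likeliest explanation and not an established one. The shortfall does not depend on it: whatever the source, 80% is not the power of the planned test.
- **The plan calls its assumptions simplifying.** It does, but they simplify the true rates. They do not remove the sampling error of the pre-period groups.
- **No rule says that a non-significant interaction means no effect.** True. The plan states only what would support its hypothesis, and it already intends to report confidence intervals for the differential change. Misreading is a risk that the power statement creates, not an instruction in the plan.
- **Scale matters.** The power figures above are for the logit interaction. An interval for differential change in proportions is a different criterion, with lower power of about 42%, 47% and 50% for the three pairs. This stands, and is why the interaction odds ratio and its interval need to be reported beside it.
- **The numbers cannot change.** This is a chart review whose size follows from expected counts, and the document is dated after the patient window closed. This limits the remedy to wording, but it does not make the stated figure correct.

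**Conclusion.** The concern holds. For the test that decides the primary maternal question, power is about 53–55% and not 80% for each of the three pairs of rates in section 4.g. The overstatement is about 25 percentage points, and the chance of missing each effect is about 45–47% instead of 20%.

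This rests on the plan's own assumptions about the four rates, on 120 patients being reached in every group (the plan gives these as expected counts), and on a model without covariates. The design issue applies equally to the infant composite. The documents give no infant base rate, so no infant power figure can be derived from them.

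**What to change.** Replace the maternal power statement in section 4.g with wording such as:

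> With 120 patients per group, equal pre-period rates and no change at Methodist, the hospital-by-time interaction (two-sided 0.05, no covariates) has about 54% power for 20% vs 8%, 30% vs 15% and 40% vs 23%. It has 80% power (simulated Wald test) for Regions post-period rates of about 5%, 11% and 18% respectively.

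Add to section 4.f that the interaction odds ratio and its 95% CI will be reported alongside the planned interval for differential change. Add also that a non-significant interaction will be interpreted from these intervals, and not as a negative result from a study with 80% power. The odds ratio interval is the one on the same scale as the test.

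For the infant composite, say that the same issue applies and that the detectable difference depends on a base rate not yet given.

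The cost is a change of wording and a less favourable power figure. No extra patients are needed and the planned model does not change.

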research question 2.1. The simulation center and medical staff will also contact staff for a survey 6 months following the simulation for the QI project. With an expected response rate to the first and second surveys of 100% (because staff are surveyed at the simulation event), we will have n=120 complete first and second surveys. The response rate for the 6 month survey is expected to be 80%, yielding 96 surveys for this time period.

c. Data collection process

i. Data sources: Data sources for this study are: 1. Data pull from HP electronic medical record; 2. chart review; and 3. medical staff surveys from the simulation QI project.

Patient sample: A Clarity pull of EMR data by the Institute RIIS programmer will gather many of the needed data elements. For data elements not readily available with a programmatic data pull, two University of Minnesota medical students along with [name] will conduct manual chart reviews of 640 patients to obtain the needed data elements (see outcomes table below).

Staff sample: Staff-provided information from the simulation QI project. Pre and post electronic surveys of medical staff at the time of the simulation event as well as email surveys 6 months after the simulation event. Surveys will be administered using REDCap. These data collection activities are being done for a QI project, but this QI project data will be used to address research question 2.1

ii. Process steps for identification of patients or records:

Patient data: The study programmer (HP Institute RIIS programmer) will use the inclusion criteria specified earlier and used for the preliminary data counts to gather patient data on the expected 640 patients who are expected to be study-eligible at Regions and Methodist Hospitals in the pre and post-simulation periods. The data pull for patient identification will occur at multiple times to accommodate data needs for specific research questions. A chart review (described below) will be conducted to gather additional morbidity data.

iii. Process steps for data acquisition

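### The six-month staff survey is planned at 96 in two places and 80 in a third, and the 0.32 SD detectable change printed for 96 fits 80 (96 gives 0.29).

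*Combined protocol and SAP*

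**What the plan says.** Three places in the combined protocol and SAP bear on the six-month staff survey.

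- **Section 4(b)(ii), medical staff sample size.** All 120 staff are expected to complete the surveys before and after the simulation: "we will have n=120 complete first and second surveys". For the later survey: "The response rate for the 6 month survey is expected to be 80%, yielding 96 surveys for this time period".
- **Section 4(f), research question 2.1, analytic sample.** The comparison of baseline with six months is planned on a "sample of 80 completing the pre and 6 month surveys". The analysis is mainly descriptive. On testing it says: "Simple paired-data analyses (e.g., paired t-tests, McNemar's test) may be used to test change over time".
- **Section 4(g), power analysis.** One sentence gives two detectable changes for a continuous survey item. The first is for the two surveys taken at the event itself: "0.26 standard deviation units for the sample of n=120 (pre to post simulation"). The second is for contrasts with the later survey: "0.32 standard deviation units for the sample of n=96 (pre to 6 months, or post to 6 months").

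Nothing in the documents explains the 80 or reconciles it with the 96.

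**The concern.** Two things do not fit. First, the same group of respondents is 96 in sections 4(b)(ii) and 4(g) but 80 in section 4(f). Second, the step from 0.26 SD to 0.32 SD is too large for a drop from 120 to 96 respondents, and about right for a drop to 80.

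Provider confidence is a named secondary aim, and the six-month survey is the only look at whether any gain lasts. As written, a reader cannot tell how many paired responses were planned, has two denominators against which to judge the response achieved, and is given a sensitivity that does not belong to the sample printed beside it.

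**Working it through.** **Inputs**

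- Staff surveyed: 120; six-month response: 80% (section 4(b)(ii)).
- Six-month sample: 96 (sections 4(b)(ii) and 4(g)) or 80 (section 4(f), research question 2.1).
- Test: paired t-test, the example named in section 4(f).
- Alpha and power: "this study is powered at 80% (alphas=.05, 2-sided"). Section 4(g) states these for the patient comparison and does not restate them for the survey. Carrying them over is an assumption, which step 2 tests.
- SD unit: taken as the SD of the within-person change. The plan does not define it.

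**Step 1. Sample size.** 0.80 × 120 = 96. If 80 is meant, the response is 80/120 = 66.7%.

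**Step 2. Detectable change.** For n pairs and a standardised change δ, power is the probability that a non-central t variable with n − 1 degrees of freedom and non-centrality δ√n exceeds the two-sided 5% critical value. Setting power to 0.80 and solving for δ gives the second column below. The third column is the normal approximation, δ = (1.960 + 0.842)/√n = 2.802/√n.

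| n | δ, paired t | δ, normal approximation | Plan prints |
|---|---|---|---|
| 120 | 0.258 | 0.256 | 0.26 |
| 96 | 0.289 | 0.286 | 0.32 |
| 80 | 0.317 | 0.313 | no figure given for 80 |

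The plan's figure for 120 is reproduced, which supports the assumed settings. Its figure for 96 is not. The paired-t value for 80 rounds to 0.32.

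**Step 3. Power at the printed changes (paired t).** 0.26 SD with n = 120: 80.7%. 0.32 SD with n = 96: 87.4%. 0.32 SD with n = 80: 80.7%. The smallest n with 80% power at 0.32 SD is 79.

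**Step 4. Does this depend on the assumed alpha and power?** Under any settings shared by the two survey figures, the detectable change varies essentially as 1/√n. Take the first figure at its upper rounding limit, 0.265. Then n = 96 gives at most about 0.265 × √(120/96) = 0.265 × 1.118 = 0.296, which cannot round to 0.32.

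In the other direction, the two printed figures with full rounding allowance imply a second sample between

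- 120 × (0.255/0.325)² = 73.9 and
- 120 × (0.265/0.315)² = 84.9.

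That range contains 80 and excludes 96.

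**Step 5. Other settings, n = 96.** One-sided testing gives 0.256; 85% power, 0.309; 90% power, 0.334; alpha 0.01, 0.355; a Wilcoxon efficiency adjustment, 0.296 to 0.311; two independent groups of 96, 0.404. None rounds to 0.32. Two settings do: alpha 0.025 (0.319), and scaling by the raw-score SD with a within-person correlation of about 0.39. At n = 120 they give 0.284 and about 0.285, so neither also yields the printed 0.26.

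**The case against.** The best case on the other side is that this hardly matters. Research question 2.1 is secondary, and section 4(f) treats inference on secondary endpoints as exploratory. Its analysis is mainly descriptive, with paired tests optional. All 120 required attendees are surveyed, so no sample size was chosen from this figure. The printed 0.32 SD also never overstates sensitivity: it has about 81% power with 80 pairs and 87% with 96. All of this stands, and it limits the weight of the point.

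It can also be said that the documents show only that three numbers disagree, not which is wrong. This stands in part. That 0.32 was computed with 80, or that 80 came from reading the 80% as a count, is inference. A different alpha or correlation used only for the six-month contrast could also give 0.32 at 96, but both survey figures sit in one sentence and no such change is stated.

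A kinder reading is that 96 surveys come back and only 80 of them (80/96 = 83%) can be matched to a baseline survey. The plan does not say this. It expects every attendee to have a baseline survey, and section 4(g) uses 96 for the change from baseline. Matching is still a fair question, because the staff survey paragraph mentions a before/after label but no personal identifier.

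Finally, the six-month survey was scheduled for June 2018 and the document is dated July 30, 2019. If the survey ran on schedule, the achieved number was already available and would inform more than a corrected expectation. That adds to the fix and does not answer the discrepancy.

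**Conclusion.** The point holds on both counts. The six-month sample is stated inconsistently, 96 against 80, a difference of 16 respondents or of 80% against 67% response. The 0.32 SD does not belong to 96: by the method that reproduces the plan's figure for 120, 96 gives 0.29 SD and 80 gives 0.32 SD.

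The contradiction between 96 and 80 needs no assumption. The exact 0.29 rests on a paired t-test with two-sided alpha 0.05, 80% power and the SD of the within-person change. The narrower conclusion, that 0.32 cannot go with 96 if 0.26 goes with 120, needs only that both figures share the same settings.

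The size is small, about 0.03 SD in the conservative direction, and neither primary analysis is touched. It is still worth correcting, because a stated sample and its stated sensitivity do not match.

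**What to change.** Choose one six-month sample and carry it through.

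- **If 96 is the expectation** (it follows from the stated 80% response): change 80 to 96 in the research question 2.1 analytic sample, and 0.32 to 0.29 SD in section 4(g).
- **If 80 is the expectation:** keep 0.32 SD, change 96 to 80 in section 4(g), and in section 4(b)(ii) change both the 80% response to 67% and the resulting 96 surveys to 80. If the 80 reflects matching losses among 96 returns, say so instead of changing the response rate.

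In either case, state in section 4(g) that the survey figures use two-sided alpha 0.05 and 80% power, and that the SD is that of the within-person change. If the six-month survey has been completed, report the achieved number of matched pairs alongside.

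The cost is a few numbers and a sentence of text. The design, data collection and analysis method stay as they are.
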